5.3. Screen Failures

Patients who are entered into the study but do not meet the enrollment criteria for participation in this study (screen failure) may be re-screened once. The interval between screen failure and re-screenings should be at least 4 weeks. At the time of re-screening, the individual must sign a new ICF, repeat all necessary screening procedures, and will be assigned a new identification number.

5.4. Lifestyle and/or Dietary Requirements

Study participants should be instructed not to donate blood or blood products during the study or for 30 days following the last dose of investigational product.

6. Treatment

6.1. Treatments Administered

This study involves a comparison of baricitinib 4-mg and baricitinib 2-mg administered orally once daily with placebo. [Table JAHH.2](#) shows the treatment regimens.

Table JAHH.2. Treatment Regimens

Regimen	Dose Week 0 through Week 24
Baricitinib 4-mg QD	1 baricitinib 4-mg tablet and 1 placebo tablet matching baricitinib 2-mg
Baricitinib 2-mg QD	1 baricitinib 2-mg tablet and 1 placebo tablet matching baricitinib 4-mg
Placebo	2 placebo tablets: 1 matching baricitinib 4-mg and 1 matching baricitinib 2-mg

Abbreviations: QD = daily.

The investigator or his/her designee is responsible for the following:

- explaining the correct use of the investigational product to the patient or legal representative
- verifying that instructions are followed properly
- maintaining accurate records of investigational product dispensing and collection
- at the end of the study, returning all unused medication to Lilly, or its designee, unless the sponsor and sites have agreed all unused medication is to be destroyed by the site, as allowed by local law.

6.2. Method of Treatment Assignment

Patients who meet all criteria for enrollment will be randomized in a 1:1:1 ratio (baricitinib 4-mg; baricitinib 2-mg; placebo) to double-blind treatment at Visit 2 (Week 0). Randomization will be stratified by disease activity (SLEDAI-2K <10; SLEDAI-2K ≥10), anti-dsDNA status (positive; negative), and region (defined in the SAP). Assignment to treatment groups will be determined by a computer-generated random sequence using an interactive web-response system (IWRS). The IWRS will be used to assign 2 bottles (Bottle A and Bottle B), each containing 36 double-blind investigational product tablets to each patient, starting at Visit 2 (Week 0), and at each visit through Visit 8 (Week 20). Site personnel will confirm that they have located the correct bottles by entering a confirmation number found on the bottles into the IWRS. Patients will be instructed to take 1 tablet from Bottle A and 1 tablet from Bottle B each day.

6.2.1. Selection and Timing of Doses

The investigational product (1 tablet from Bottle A and 1 tablet from Bottle B) should be taken without regard to food and, if possible, at approximately the same time every day to aid patient compliance. Refer to Section 8.5, Pharmacokinetics, for specific instructions on dose timing at certain visits where a PK sample is drawn.

6.3. Blinding

This is a double-blind study. All study assessments will be done by study personnel who are blinded to the patient's treatment group. Except in clinical circumstances where unblinding is required, the patients, investigators, Lilly study team, and any personnel interacting directly with patients or investigative sites will remain blinded to baricitinib and placebo assignment until after completion of the Double-Blinded Treatment Period. It is expected that the need for unblinding a patient's treatment prior to completion of the Double-Blinded Treatment Period will be extremely rare. Every effort should be made to preserve the blind unless there is a compelling reason that knowledge of the specific treatment would alter the medical care of the patient.

Emergency unblinding for AEs may be performed through the IWRS. This option may be used ONLY if the patient's acute well-being requires knowledge of the patient's treatment assignment. All unblinding events are recorded and reported by the IWRS.

In case of an emergency, the investigator has the sole responsibility for determining if unblinding of a patient's treatment assignment is warranted. Patient safety must always be the first consideration in making such a determination. If the investigator decides that unblinding is warranted, the investigator should make every effort to contact the Lilly clinical research physician (CRP) or designee prior to unblinding a patient's treatment assignment unless this could delay emergency treatment of the patient. If a patient's treatment assignment is unblinded, Lilly must be notified immediately.

If an investigator, site personnel performing assessments, or patient is unblinded, patient discontinuation should be considered after discussion with the sponsor. In cases where there are ethical reasons to have the patient remain in the study, the investigator must obtain specific approval from the Lilly CRP for the patient to continue in the study.

6.4. Packaging and Labeling

The sponsor (or its designee) will provide the following investigational products:

- tablets containing 4-mg of baricitinib (Bottle A)
- tablets containing 2-mg of baricitinib (Bottle B)
- placebo tablets to match baricitinib 4-mg tablets (Bottle A)
- placebo tablets to match baricitinib 2-mg tablets (Bottle B).

Baricitinib 4-mg and 2-mg tablets and packaging will be identical in appearance to the respective placebo tablets in order to maintain the blind.

Investigational product tablets will be provided in bottles containing 36 tablets.

Clinical trial materials will be labeled according to the country's regulatory requirements.

6.5. Preparation/Handling/Storage

All investigational product (used and partially used) will be returned to the sponsor or destroyed at site level with the sponsor's written approval. In some cases, sites may destroy the material if,

during the investigative site selection, the evaluator has verified and documented that the site has appropriate facilities and written procedures to dispose of clinical trial materials.

Follow storage and handling instructions on the investigational product packaging.

6.6. Dose Modification

Not applicable.

6.7. Treatment Compliance

Patient compliance with investigational product will be assessed at each visit during the treatment period (Visit 3 through Visit 9) by counting returned tablets. Deviations from the prescribed dosage regimen should be recorded in the electronic case report form (eCRF).

A patient will be considered significantly noncompliant if he or she misses more than 20% of the prescribed doses of investigational product (full doses) during the study, unless the patient's investigational product is withheld by the investigator for safety reasons. Similarly, a patient will be considered significantly noncompliant if he or she is judged by the investigator to have intentionally or repeatedly taken 20% more than the prescribed amount of medication.

Patients will be counseled by study staff on the importance of taking the investigational product as prescribed, as appropriate.

Patients' compliance will be further defined in the SAP.

6.8. Concomitant Therapy

Patients will maintain their usual medication regimen for SLE and for any other concomitant diseases throughout the study unless specifically excluded in the protocol (see Section 5.2, Exclusion Criteria). Patients taking these medications should be on chronic stable doses at the time of randomization, as specified by the Entry Criteria (Section 5.2.1).

Concomitant SoC for SLE in this study can include corticosteroids, NSAIDs, a single antimalarial (such as chloroquine or hydroxychloroquine), and/or a single immunosuppressant (such as azathioprine, MTX, or mycophenolate).

Corticosteroid dose must be ≤ 20 -mg per day of prednisone (or equivalent) and stable for 2 weeks prior to randomization. Increases in corticosteroid dose are not permitted after randomization. Decreases in corticosteroid dose will be permitted between Week 0 and Week 16. If corticosteroid dose is decreased during this time period, subsequent increases, only to less than or equal to the baseline dose, will be permitted until Week 16. No changes in corticosteroids (increases or decreases) will be permitted between Week 16 and Week 24. Patients who require initiation or increase in dose of corticosteroids after randomization should be discontinued from investigational product, have an ETV, and proceed to the Follow-Up Period of the study.

Doses of NSAIDs (for which the NSAID use is intended for treatment of signs and symptoms of SLE), antimalarials, and immunosuppressants should not be adjusted during the Double-Blinded Treatment Period. Patients who require initiation or increase in dose of NSAIDs (for which the

NSAID use is intended for treatment of signs and symptoms of SLE), antimalarials, or immunosuppressants after randomization should be discontinued from investigational product, have an ETV, and proceed to the Follow-Up Period of the study.

Any changes to the patient's medication must be discussed with the investigator. Patients should be instructed to consult the investigator or other appropriate study personnel at the site before taking any new medications or supplements.

Additional medications are to be avoided during the study unless required to treat an AE or for the treatment of an ongoing medical problem. If the need for concomitant medication arises, inclusion or continuation of the patient may be at the discretion of the investigator after consultation with Lilly or its designee. Any additional medication, whether prescription or over-the-counter, used at baseline and/or during the course of the study must be documented in the eCRF with start and stop dates.

6.9. Treatment after Study Completion

6.9.1. Continued Access

Baricitinib will not be made available after conclusion of the study. Patients will be referred to their local treatment centers for continued therapy as clinically indicated.

7. Discontinuation Criteria

7.1. Discontinuation from Study Treatment

7.1.1. Interruption of Investigational Product

In some circumstances, it may be necessary to temporarily interrupt treatment as a result of AEs or abnormal laboratory values that may have an unclear relationship to investigational product. Except in cases of emergency, it is recommended that the investigator consult with Lilly (or its designee) before temporarily interrupting therapy for reasons other than those defined in [Table JAHH.3](#) below. Retest timing and frequency is at the investigator's discretion.

The investigator must obtain approval from Lilly (or its designee) before restarting investigational product that was temporarily discontinued because of an AE or abnormal laboratory value. Investigational product must be held in the following situations and may be resumed as noted in [Table JAHH.3](#).

Table JAHH.3. Criteria for Temporary Interruption of Investigational Product

Hold investigational product if the following laboratory test results occur:	Investigational product may be resumed after approval from Lilly (or its designee) when:
WBC count <2000 cells/ μ L (<2.00x10 ³ / μ L or <2.00 GI/L)	WBC count \geq 2500 cells/ μ L (\geq 2.50x10 ³ / μ L or \geq 2.50 GI/L)
ANC <1000 cells/ μ L (<1.00x10 ³ / μ L or <1.00 GI/L)	ANC \geq 1200 cells/ μ L (\geq 1.20x10 ³ / μ L or \geq 1.20 GI/L)
Lymphocyte count <500 cells/ μ L (<0.50x10 ³ / μ L or <0.50 GI/L) Note: IP can be continued with a lymphocyte count <500 cells/ μ L but \geq 300 cells/ μ L (<0.30x10 ³ / μ L or <0.30 GI/L) if the low lymphocyte count is considered by the investigator to be a result of the underlying SLE disease or concomitant medications. IP must be held for lymphocyte count <300 cells/ μ L, regardless of cause.	Lymphocyte count \geq 750 cells/ μ L (\geq 0.75x10 ³ / μ L or \geq 0.75 GI/L) Note: If IP is held for lymphocyte count <300 cells/ μ L, it may be resumed after approval from Lilly (or its designee) when the lymphocyte count is \geq 500 cells/ μ L if the low lymphocyte count is considered by the investigator to be a result of the underlying SLE disease or concomitant medications.
Platelet count <25,000/ μ L (<25x10 ³ / μ L or <25 GI/L)	Platelet count \geq 50,000/ μ L (\geq 50x10 ³ / μ L or \geq 50 GI/L)
eGFR <40 mL/min/1.73 m ² (from serum creatinine)	eGFR \geq 50 mL/min/1.73 m ²
ALT or AST >5 x ULN	ALT and AST return to <2 x ULN, and IP is not considered to be the cause of enzyme elevation
Hemoglobin <8 g/dL (<80.0 g/L)	Hemoglobin \geq 9 g/dL (\geq 90.0 g/L)
Symptomatic herpes zoster	All skin lesions have crusted and are resolving
Severe infection that, in the opinion of the investigator, merits the IP being discontinued	Resolution of infection

Abbreviations: ALT = alanine aminotransferase; ANC = absolute neutrophil count; AST = aspartate aminotransferase; eGFR = estimated glomerular filtration rate; IP = investigational product; ULN = upper limit of normal; WBC = white blood cell.

7.1.2. *Permanent Discontinuation of Investigation Product*

Any patient who is permanently discontinued from investigational product for an AE or abnormal laboratory result should have the reason for investigational product discontinuation reported as the AE or abnormal laboratory value.

Discontinuation of the investigational product for abnormal liver tests **should be considered** by the investigator when a patient meets one of the following conditions after consultation with the Lilly designated medical monitor:

- ALT or AST >8 x ULN
- ALT or AST >5 x ULN for more than 2 weeks after temporary interruption of investigational product
- ALT or AST >3 x ULN and either total bilirubin level (TBL) >2 x ULN or INR >1.5 x ULN
- ALT or AST >3 x ULN with the appearance of fatigue, nausea, vomiting, right upper-quadrant pain or tenderness, fever, rash, and/or eosinophilia (>5%)
- alkaline phosphatase (ALP) >3 x ULN
- ALP >2.5 x ULN and TBL >2 x ULN
- ALP >2.5 x ULN with the appearance of fatigue, nausea, vomiting, right upper quadrant pain or tenderness, fever, rash, and/or eosinophilia (>5%).

Patients should be discontinued from the investigational product in the following circumstances:

- WBC count <1000 cells/ μ L ($1.00 \times 10^3 / \mu$ L or 1.00 GI/L)
- ANC <500 cells/ μ L ($0.50 \times 10^3 / \mu$ L or 0.50 GI/L)
- Lymphocyte count <200 cells/ μ L ($0.20 \times 10^3 / \mu$ L or 0.20 GI/L)
- Hemoglobin <6.5 g/dL (<65.0 g/L).

For lab values that meet permanent discontinuation thresholds, investigational product should be discontinued unless, in the opinion of the investigator, the lab abnormality is due to intercurrent illness or another identified factor. After consultation with the Lilly-designated medical monitor, the patient may be able to continue receiving investigational product. Lab tests may be repeated within 1 week to confirm whether discontinuation criteria have been met. Furthermore, if investigational product is not discontinued due to intercurrent illness, the investigator must confirm the lab value no longer meets discontinuation thresholds following the resolution of the intercurrent illness or other identified factor.

In addition, patients will be discontinued from investigational product in the following circumstances:

- Pregnancy

- Malignancy (except for successfully treated basal cell or squamous epithelial skin cancers)
- HBV DNA above the lower limit of quantification (LLOQ)

Note: If the HBV DNA result is “target detected” (above the LLOQ), then the patient should be referred to a hepatology specialist immediately. In selected cases, investigators may temporarily continue investigational product in accordance with current immunomodulator management in the setting of HBV DNA positivity. This option may be considered in consultation with Lilly (or its designee) and evaluation of individual patient risks and benefits. Refer to Section 8.4.4 for additional instruction on HBV DNA monitoring.

Some possible reasons that may lead to permanent discontinuation include:

- Enrollment in any other clinical trial involving an investigational product or enrollment in any other type of medical research judged not to be scientifically or medically compatible with this study
- Participation in the study needs to be stopped for medical, safety, regulatory, or other reasons consistent with applicable laws, regulations, and good clinical practice (GCP)
- Investigator Decision
 - the investigator decides that the patient should be discontinued from the study
 - if the patient, for any reason, requires treatment with another therapeutic agent that has been demonstrated to be effective for treatment of the study indication (including initiation or increase in dose of NSAIDs [for which the NSAID use is intended for treatment of signs and symptoms of SLE], corticosteroids [above the baseline dose], antimalarials, and/or immunosuppressants) discontinuation from the investigational product occurs prior to introduction of the new agent
- Patient Decision
 - the patient requests to be withdrawn from the study.

Patients who discontinue the investigational product early will have ETV procedures performed as shown in the Schedule of Activities ([Appendix 2](#)) and proceed to the Follow-Up Period of the study.

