8.2.2. Adverse Events and Laboratory Tests of Special Interest (AESIs)

Adverse events of special interest (AESIs) or laboratory results of special interest will include severe or opportunistic infections; myelosuppressive events of anemia, leukopenia, neutropenia, lymphopenia, and thrombocytopenia; thrombocytosis; and elevations in ALT or AST (>3 x ULN) and total bilirubin (>2 x ULN).

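### Table JAHH.3 requires a hold for isolated ALT or AST >5 x ULN but not for ALT or AST >3 to 5 x ULN with raised bilirubin (or INR), which Section 7.1.2 lists as grounds for considering permanent discontinuation

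*Protocol*

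**What the plan says.** Protocol Section 7.1.1 makes the temporary holds compulsory: "Investigational product must be held in the following situations and may be resumed as noted in" Table JAHH.3. The table's only liver-test row is "ALT or AST >5 x ULN". Dosing may resume with sponsor approval once ALT and AST are below 2 x ULN and product is not thought to be the cause. For interruptions outside the table, "it is recommended that the investigator consult with Lilly (or its designee) before temporarily interrupting therapy for reasons other than those defined in" the table, except in an emergency.

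Section 7.1.2 gives seven liver conditions. One is "ALT or AST >3 x ULN and either total bilirubin level (TBL) >2 x ULN or INR >1.5 x ULN". Permanent discontinuation is to be considered "by the investigator when a patient meets one of the following conditions after consultation with the Lilly designated medical monitor". After a separate list of blood-count stopping limits comes a general paragraph: "For lab values that meet permanent discontinuation thresholds, investigational product should be discontinued unless, in the opinion of the investigator", puts the abnormality down to a concurrent illness or another identified cause. The patient may be able to continue after consultation with the medical monitor. It adds: "Lab tests may be repeated within 1 week to confirm whether discontinuation criteria have been met".

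Section 8.2.2 includes "elevations in ALT or AST (>3 x ULN) and total bilirubin (>2 x ULN") among the results of special interest. Section 8.4.7 starts clinical and laboratory monitoring and contact with the sponsor's physician from ALT 3 x ULN or total bilirubin 2 x ULN, but states no hold.

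**The concern.** The compulsory hold and the grounds for permanent stopping are out of order for liver tests. A transaminase rise on its own must be held at a level that does not by itself raise permanent stopping. A lower transaminase rise with raised bilirubin does raise permanent stopping, yet it triggers no compulsory hold. The bilirubin and transaminase cut-offs involved are ones the sponsor already singles out in Section 8.2.2.

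What is at stake is patient safety during a short interval: the days between the first abnormal result and the decision reached after consultation and any retest. A site that keeps dosing through those days can fairly say that it followed the protocol. Sample size, power and type I error are not affected.

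**Working it through.** There is no plan figure to reproduce. The check sets the thresholds side by side.

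**Inputs.** The hold rule comes from Section 7.1.1 and Table JAHH.3, and the seven liver conditions and the blood-count limits from Section 7.1.2. The screening limits come from exclusion [60] in Section 5.2.2, the nonresponder rule from Section 9.2.4, and the arm size and design rates from Section 9.1.

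**Step 1: five cases.** Analytes not mentioned are taken as normal, and each is a first result.

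| Case | Mandatory hold? | Liver conditions met in 7.1.2 |
|---|---|---|
| ALT 5.1 x ULN, no symptoms | Yes | 0 of 7 |
| ALT 4 x ULN, bilirubin 2.5 x ULN | No | 1 of 7 |
| ALT 4 x ULN, INR 1.6 x ULN | No | 1 of 7 |
| ALT 4 x ULN with a listed symptom | No | 1 of 7 |
| ALT 6 x ULN, bilirubin 2.5 x ULN | Yes, through the >5 x ULN row | 1 of 7 |

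The uncovered band for the combination is therefore ALT or AST above 3 and up to 5 x ULN. Above 5 x ULN the existing row already applies.

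**Step 2: which conditions lie inside the hold.** Two of the seven lie wholly inside it: above 8 x ULN, and above 5 x ULN for more than 2 weeks after interruption. The two conditions that start at 3 x ULN (with bilirubin or INR, and with symptoms) lie inside it only above 5 x ULN. The three alkaline phosphatase conditions have no hold row.

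**Step 3: the blood counts.** The stop limit against the mandatory hold limit is:
- white cells: 1000 against 2000 per µL
- neutrophils: 500 against 1000 per µL
- lymphocytes: 200 against 300 per µL (held whatever the cause)
- hemoglobin: 6.5 against 8 g/dL

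All 4 of 4 stop limits lie inside a mandatory hold, so product is already withheld when permanent stopping comes up. The liver combination departs from this pattern.

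**Step 4: exposure.** Dosing is once daily. If product is not held and the retest takes place within 7 days, the patient takes 0 to 7 further doses. The most is 7 x 4 mg = 28 mg or 7 x 2 mg = 14 mg.

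**Step 5: cost to the primary endpoint.** A temporary hold is not itself nonresponse under Section 9.2.4; discontinuation is. One extra discontinuation lowers an arm's remission rate by at most 1/100 = 1 percentage point. Weighted by the design rates, the average is 0.40 x 1 = 0.4 points on placebo and (0.40 + 0.20) x 1 = 0.6 points on active drug, against a design difference of 20 points.

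**The case against.** The strongest reply is that the general paragraph of Section 7.1.2 already does more than a hold. Read naturally, it makes stopping the default for any laboratory value at a permanent threshold, with continuation possible only after the monitor is consulted. It does not say that dosing goes on while the test is repeated. Investigators may also hold outside the table, and Section 8.4.7 brings in the sponsor from ALT 3 x ULN. A reader might infer that the protocol directs dosing to continue, or is silent on dosing until the decision. These provisions do not support either reading.

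The conflict remains. For liver tests the specific instruction is only to consider stopping, after consultation. The general paragraph, which follows the blood-count list, says to stop unless another cause is found, and also allows a confirmatory retest. Section 7.1.1 recommends speaking to the sponsor before a hold outside the table. A site can reconcile these by continuing to dose until the call and the retest are done.

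The reply also notes that a temporary rule is meant to catch results short of permanent stopping, so a hold at isolated ALT 5.1 x ULN is no anomaly. That is correct. The fault is the missing hold for the combination. A further objection, that ALT or AST above 3 x ULN with symptoms has the same gap, is also correct, and the fix takes it in.

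Appendix 4 (hepatic monitoring tests) is not in the text available. Its title and the reference in Section 8.4.7 point to tests, but a dosing instruction there cannot be ruled out. INR is not in the Appendix 3 test list, so how the INR half would work in practice cannot be checked; the bilirubin half does not depend on it.

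**Conclusion.** The concern stands as an inconsistency between the interruption and discontinuation rules that is cheap to remove. In the text available, ALT or AST above 3 and up to 5 x ULN with bilirubin above 2 x ULN (or INR above 1.5 x ULN if measured) carries no mandatory hold, and the two provisions in Section 7.1.2 that bear on it do not agree.

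The size is small. Seven doses assumes a retest on the last allowed day, no hold by the investigator and no intervention by the monitor. It is illustrative only, because the retest is optional and the consultation has no stated time limit. The number of patients is not given. It is probably low, since exclusion [60] bars ALT or AST above 2 x ULN and bilirubin of 1.5 x ULN or more at screening.

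**What to change.** Add one row to Table JAHH.3.

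- **Hold:** ALT or AST above 3 x ULN with total bilirubin above 2 x ULN (or INR above 1.5 x ULN where available), until the Section 7.1.2 consultation, any retest and the decision are complete.
- **Resume, with sponsor approval:** ALT and AST below 2 x ULN, bilirubin below 1.5 x ULN, any measured INR no longer above 1.5 x ULN, and product not considered the cause.

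The transaminase level and the causality condition repeat the existing liver row. The bilirubin level matches exclusion [60].

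State that the row does not replace the discontinuation default in Section 7.1.2. Apply the same interim hold to ALT or AST above 3 x ULN with the listed symptoms, or say why not. One possible reason is that rash is among those symptoms and is also a qualifying disease feature under enrollment criterion [8], so attribution may be harder.

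The cost is a table row and a few short interruptions. Monitor consultation is already part of 7.1.2, and Section 6.7 exempts doses withheld by the investigator for safety from the noncompliance count. Some holds may become discontinuations, because resumption requires that product is not considered the cause. Each would count as nonresponse, at the cost shown in the working, and some of these patients would have been discontinued anyway.
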